In addition, an efficacy interim analysis for the primary outcome will be carried out when 20 patients are enrolled in each group. The results will be provided to the DSMB committee to determine whether one method is truly inferior to the other before enrollment continues (see section on Early stopping rules below). The determination will be based on comparing the average AUC of VAS for 0-48 hours postoperative. Of the two co-primary endpoints, equivalent pain intensity scores is harder to achieve and is the more clinically relevant one. Interim analysis of toxicity, outcome and ongoing scientific investigations will be performed at least annually by the Sidney Kimmel Comprehensive Cancer Center Data Safety Monitoring Board (SKCCC DSMB). The SKCCC DSMB Recommendation letter will state the timeline for the next required review. The SKCCC DSMB will review aspects of this trial that are outlined in the responsibilities section of the Data and Safety Monitoring Board (DSMB) Guidance. If the committee decides that amendments should be made to this trial, recommendations will be made in writing to the Study Principal Investigator. The study team will submit modifications to the IRB within 60 days of receipt from the DSMB. The Associate Director of Clinical Research, will arbitrate any disagreements between the DSMB and the study Principal Investigator. These changes may include early termination of accrual if deemed appropriate. The SKCCC Compliance Monitoring Program will provide external monitoring for JHU-affiliated sites in accordance with SKCCC DSMP (Version 6.0, 02/21/2019). The SMC Subcommittee will determine the level of patient safety risk and level/frequency of monitoring.

b. Study duration and number of study visits required of research participants.

Patients will be considered to be "on study" for the duration of their inpatient hospitalization and for 14 days postoperatively. Each participating individual will have no extra or additional outpatient study visits.

c. Blinding, including justification for blinding or not blinding the trial, if applicable.

Because of the invasive nature of the interventions, neither the trial participants nor the investigators will be masked to group allocation.

d. Justification of why participants will not receive routine care or will have current therapy stopped.

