The study is powered for the primary outcome of Area under the Curve (AUC) for pain from 0-48 hours. From review of the literature of previous studies, we deemed a margin of 80% of 48 hours to be non-inferior [24,25,]. A group sample size of 50 per cohort is needed achieve a 90% power to detect non-inferiority using a one-sided, Mann-Whitney test. The margin of non-inferiority is 38 (80% of 48 hours). The non-inferiority margin corresponds to an increase in pain, not a decrease. The pain VAS ranges from 0 to 10, with 10 being the worst pain. Therefore, non-inferiority will be declared if the average AUC for liposomal bupivacaine is no more than 38 units compared to the average AUC in the TEA group. The true difference between the means is assumed to be 0.0. The significance level (alpha) of the test is 0.025 and the data are drawn from populations with standard deviations of 55.0. These assumptions were derived from previous Pacira studies. It is reasonable to assume that the standard deviation of the AUC for 0-48 hours is about 55 units and the difference between the groups is 0. Sample size calculations were performed using PASS (PASS 16 Power Analysis and Sample Size Software (2018). NCSS, LLC. Kaysville, Utah, USA, ncss.com/software/pass). Of note, with sequential testing of the co-primary endpoints, the study remains to be adequately powered with the addition of the total opioid consumption co-primary endpoint. A sample size of 50 participants in each arm will have adequate power (>90%) to detect non-inferiority with a margin of 21.2 IV morphine equivalents using a one-sided test with a common standard deviation of 25 and alpha of 0.025. The non-inferiority margin was determined by the clinically significant threshold of 10.6 mg in daily IV morphine equivalent dose [24], therefore, 21.2 morphine equivalent dose for over 2 days (0-48 hours).

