If there is concern for harm on either arm of the study this will be immediately discussed with the PI and the study will be stopped until the concern is resolved. The PI will internally monitor the progress of the trial, including review and confirmation of all safety/treatment-related outcomes, response assessments, safety reports and/or any related source documentation. As per above, the DSMB will meet after 20 patients have been enrolled in each arm. Regarding the futility boundary for the interim analysis – based on the results from the pilot study in 2019, the pain for the Epidural group and for the Exparel group are about the same (3.9 vs 4.0 in a 0-10 scale). With the O'Brien-Fleming futility boundary of 0.2986, there is only 0.1% chance of falsely crossing the futility boundary and stopping the study at 20 participants per arm assuming equal pain for both groups. The overall power remains to be over 90%. If in case that the Exparel group is truly inferior to the Epidural group by at least the pre-specified non-inferiority margin, there is at least a 38% chance of claiming early futility at 20 patients per arm to protect more patients from being exposed to the inferior treatment.

Interim analysis of toxicity, outcome and ongoing scientific investigations will be performed at least annually by the Sidney Kimmel Comprehensive Cancer Center Data Safety Monitoring Board (SKCCC DSMB). The SKCCC DSMB Recommendation letter will state the timeline for the next required review. The SKCCC DSMB will review aspects of this trial that are outlined in the responsibilities section of the Data and Safety Monitoring Board (DSMB) Guidance. If the committee decides that amendments should be made to this trial, recommendations will be made in writing to the Study Principal Investigator. The study team will submit modifications to the IRB within 60 days of receipt from the DSMB. The Associate Director of Clinical Research, will arbitrate any disagreements between the DSMB and the study Principal Investigator. These changes may include early termination of accrual if deemed appropriate. The SKCCC Compliance Monitoring Program will provide external monitoring for JHU-affiliated sites in accordance with SKCCC DSMP (Version 6.0, 02/21/2019). The SMC Subcommittee will determine the level of patient safety risk and level/frequency of monitoring.

1. Risks

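### The futility boundary of 0.2986 has no stated statistic, sign or direction, and its 0.1% false-stop chance does not follow from the plan's AUC inputs (about 0.65% on the reading that gives 38%)

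*Combined protocol and SAP*

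**What the plan says.** Section 4a (Study design) schedules the look: "an efficacy interim analysis for the primary outcome will be carried out when 20 patients are enrolled in each group". It names the endpoint: "The determination will be based on comparing the average AUC of VAS for 0-48 hours postoperative".

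Section 7b (Early stopping rules) gives the rule and its properties. On false stopping: "futility boundary of 0.2986, there is only 0.1% chance of falsely crossing the futility boundary and stopping the study at 20 participants per arm". The premise for that figure is that pain is the same in the two arms. On stopping an inferior treatment, meaning LB worse by at least the non-inferiority margin: "there is at least a 38% chance of claiming early futility at 20 patients per arm". On power, in percent: "The overall power remains to be over 90".

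Section 7a gives the AUC design inputs: margin 38, with a higher AUC being worse; assumed true difference 0; one-sided alpha 0.025; 50 per arm; and "the data are drawn from populations with standard deviations of 55.0". For the opioid co-primary endpoint it gives margin 21.2 mg and SD 25.

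The plan does not define the interim test statistic, the sign of the boundary or the direction of crossing. Section 4a calls the look an efficacy analysis, while Section 7b treats it as a futility look.

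**The concern.** A boundary on a known scale, together with the SD, margin and interim sample size, fixes both stopping probabilities. The plan states the boundary and both probabilities, so they can be checked against each other. On the AUC inputs they do not agree.

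Two things are at stake. First, this is the only numerical stopping rule the DSMB receives, and the members must infer how to apply it. A sign change moves the stopping point from an observed LB excess of about 43 AUC units to about 33, which is inside the margin of 38. Second, the stated assurance that an equal treatment would almost never be stopped is too optimistic for the endpoint on which the look is based.

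**Working it through.** **Inputs.** Margin 38, SD 55, true difference 0, alpha 0.025 one-sided, 50 per arm at the end (Section 7a). 20 per arm at the look, AUC endpoint (Section 4a). Boundary 0.2986, false stop 0.1%, stop at the margin at least 38%, power over 90% (Section 7b). Normal approximation throughout.

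**Final design first.** SE at 50 per arm = 55 × √(2/50) = 11.0, and 38/11.0 = 3.4545. Power = Φ(3.4545 − 1.96) = 93.2%, or 92.2% with a Mann-Whitney efficiency of 0.955. The stated 90% is met.

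**Interim scale.** SE at 20 per arm = 55 × √(2/20) = 17.39, and 38/17.39 = 2.185.

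**Reproducing the 38%.** Let Z = (mean AUC LB − mean AUC TEA − 38)/SE, with futility if Z > 0.2986.
- LB worse by exactly 38: 1 − Φ(0.2986) = 38.3%. This matches the plan.
- Equal arms: 1 − Φ(0.2986 + 2.185) = 1 − Φ(2.484) = 0.65%. The plan says 0.1%.
- Observed difference at the boundary: 38 + 0.2986 × 17.39 = 43.2 units.

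The 0.65% is stable: 0.66% with a t distribution on 38 df, 0.75% with Mann-Whitney efficiency, 0.61% with a margin of 38.4 (80% of 48), and 0.64% by simulation.

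**Is the size of the boundary plausible on this scale?** Assume O'Brien-Fleming-type beta spending with beta 0.10 at information 20/50 = 0.4. The amount spent is 2 × [1 − Φ(1.645/√0.4)] = 0.93%. For a 90% power design the boundary is then 0.303 on the Z scale above, close to 0.2986. Such a boundary itself implies a false-stop chance near 1% in a 90% power design, not 0.1%.

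**Other readings, same AUC inputs.**

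| Reading of 0.2986 | Stop if equal | Stop if LB worse by 38 |
|---|---|---|
| Z above +0.2986 | 0.65% | 38.3% |
| Z above −0.2986 (opposite sign) | 3.0% | 61.7% |
| (LB − TEA)/SE above 0.2986, no margin | 38.3% | 97.0% |
| One-sided non-inferiority p-value above 0.2986 | 4.9% | 70.1% |
| Conditional power under the design below 0.2986 | 0.13% | 20.5% |
| Conditional power under the current trend below 0.2986 | 11.4% | 83.7% |

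No row gives both stated figures.

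**Can any AUC cutoff give both?** A 0.1% false-stop chance needs an observed difference above 3.090 × 17.39 = 53.7. A trial inferior by the margin then stops with probability 1 − Φ((53.7 − 38)/17.39) = 18%. A cutoff tuned to 38% stops an equal trial 0.64% of the time. Both together need a margin/SE ratio of 3.090 − 0.305 = 2.785. That means an SD of 38/(2.785 × √0.1) = 43, or about 33 per arm at SD 55.

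**Opioid inputs.** SE = 25 × √(2/20) = 7.91, and 21.2/7.91 = 2.682. With the first sign, equal arms stop 1 − Φ(0.2986 + 2.682) = 0.14% of the time, and arms differing by the margin 38.3%. Both stated figures are matched after rounding.

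**Overall AUC power with the look** (bivariate normal, correlation √0.4). First sign: 93.0%, or 91.9% with Mann-Whitney efficiency. Opposite sign: 91.7%, or 90.5%.

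**The case against.** The strongest defence is that the rule is nearly coherent. A higher AUC is worse, so a statistic that grows as LB does worse is natural, and on that scale +0.2986 needs no correction. The boundary, the 38% and the power above 90% then all agree. Only the 0.1% fails, by about half a percentage point, and the true figure is still below 1%. Alpha, sample size and the power claim are unaffected. The result goes to a DSMB, and no automatic stop is described. All of this stands, and it limits the severity.

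A reader might go further in four ways that the documents do not support.
- *That the printed rule stops an equal trial 3% of the time and a margin-inferior one 62%.* Those figures need the opposite sign. The plan states no sign, and its own 38% points away from that one. Nor would 62% contradict a statement of at least 38%.
- *That the trial could stop on a difference of about 5 units (0.2986 × 17.39 = 5.2).* This tests against zero, whereas Section 7b ties futility to inferiority by the margin.
- *That power drops below 90%.* Simulation of the planned Mann-Whitney test gave 89.9%, but only under the opposite sign, and the analytic figure for that sign is 90.5%.
- *That 0.1% is wrong under every reading.* The opioid inputs give 0.14%, and conditional power under the design gives 0.13%. The first is for an endpoint that Section 4a does not use at the look, and conflicts with the equal-pain premise in Section 7b. The second gives 20.5% rather than 38%. The opioid match may be coincidence; the documents do not settle it.

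**Conclusion.** The point holds in a limited form. For the AUC endpoint on which the look is based, the stated 0.1% is not compatible with the stated 38%. On the only reading tried that returns 38%, the false-stop chance is about 0.65% (0.61% to 0.75% across the approximations). The boundary's statistic, sign and direction are missing and have to be inferred from the 38%. The 38% and the power above 90% are sound.

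This rests on SD 55, margin 38, exactly 20 evaluable patients per arm, and approximate normality of the mean difference. A smaller true SD, near 43, would bring the two figures together, but the plan does not assume one. Severity is minor to moderate: the numerical error is small, and the stronger reason to act is that the DSMB should not have to deduce the direction of its only numerical rule.

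**What to change.** In Section 7b, state the rule in full: endpoint AUC of VAS over 0–48 hours; Z = (mean AUC LB − mean AUC TEA − 38)/SE; futility boundary crossed if Z > 0.2986, equivalent to an observed LB excess of about 43 units if the SD is 55. Replace 0.1% with about 0.7%. Keep the 38% and the power statement. Cross-refer from Section 4a, and use one name for the look in both sections.

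Before editing, check the source calculation. If the quoted figures were produced from the opioid inputs, recompute them for AUC. If the opposite sign was intended, state about 3% and 62% instead, with AUC power of about 90% to 92%.

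The cost is a few lines of protocol text before the 20-per-arm look, with no extra patients or data.
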